7.2 General Methods

All analyses of efficacy and safety endpoints will be summarized descriptively by the two treatment groups. No statistical tests will be performed.

Randomization to the study will be stratified by site only. Any within-treatment confidence interval (CI) for the proportion analyses will be computed using normal approximation, if the number of the events in that treatment group is at least 5. Otherwise, a CI calculated using an exact method will be provided. Any between-treatment CI for the proportion difference analyses will also be computed using normal approximation, if the number of the events in each individual treatment group is at least 5. Otherwise, a CI using an exact method will be provided.

For time to event analyses, if a patient does not experience an event, the censoring will be done at the last follow-up date if the subject discontinues prematurely; otherwise, censoring will be

done at the last dose date if the subject completed the 24 month-treatment period, unless specified otherwise.

The following table provides an overview of the primary and key secondary analyses to be performed.

Table 7.2-1: Overview of Primary and Key Secondary Analyses

Measure of Interest	Analysis Method
Proportion of subjects who experience a CSBPAR at 6, 12 and 24 months post-transplant	Point estimate of the proportion and 95% CI [*] within each treatment group at 6 months.
Difference in the incidence of CSBPAR between arms, at 6, 12 and 24 months post-transplant	Point estimate and 95% CI [†] for the difference between the two arms
Time to first CSBPAR	Kaplan-Meier (KM) estimates of survival functions. Hazard Ratio and 95% CI [§]
Proportion of Subjects who survive with a functioning graft at 24 months post-transplant	Point estimate of the proportion and 95% CI [*] within each treatment group at 24 months (to be produced if there are at least 5 subjects across treatment groups who died or experienced graft loss)
Time to death or graft loss	KM estimate of subject and graft survival Hazard Ratio and 95%CI [§] (to be produced if there are at least 5 subjects across treatment groups who died or experienced graft loss)

* Confidence Interval Formula: Exact (Clopper-Pearson)

† Confidence Interval Method: Score (Wilson)

§ Using Cox Proportional Hazard model

7.3 Study Conduct

All subjects with relevant protocol deviations that could affect efficacy will be identified. A list of these protocol deviation criteria is provided in [APPENDIX 2](#). These protocol deviations are referred to as “relevant” protocol deviations in this document.

All randomized subjects with at least one relevant protocol deviation will be summarized by treatment group and overall. They will also be listed.

The ITT analysis population will be used for these analyses.

7.4 Extent of Exposure

7.4.1 Subject Disposition

The disposition of subjects will be presented as follows:

- Number of subjects enrolled at screening.
- Number of subjects randomized and transplanted, presented by randomized treatment group.
- Reasons for not being randomized.
- Number of randomized and transplanted subjects who receive at least 1 dose of Thymoglobulin and 1 dose of study treatment, either belatacept or TAC.
- Number of subjects who discontinued treatment at any time during the two years, together with reasons for discontinuation, as tabulated by randomized treatment group.
- Number of subjects continuing in the follow up phase.
- Number of subjects who discontinued study during the follow up phase, together with reasons for discontinuation and tabulated by randomized treatment group.

For the items above, the overall disposition combining all treatment groups will also be presented.

A corresponding listing of subjects who discontinued from the treatment period (including subjects randomized but not treated) and the follow up period will be provided, together with the reason for discontinuation.

The ITT analysis population will be used for these analyses.

Enrollment at each site and by age group will be summarized as specified in EudraCT requirements.

7.4.2 Demographic and Baseline Characteristics

Demographic and baseline characteristics of recipients and donors will be summarized descriptively by means and standard deviations for continuous variables, and frequency distribution for categorical variables. Summaries will be performed based on all randomized subjects (ITT population). No statistical testing will be performed to assess imbalances between the two treatment groups.

Baseline demographic characteristics include the following:

Donors and recipients

- Age in years.
- Weight in kg (recipients only).
- Height in cm at the Screening evaluation (recipients only).
- Body mass index (BMI, kg/m²) (recipients only).
- Gender: Male versus Female.
- Race.
- Ethnicity (recipients only. Only for USA subjects).
- Geographic Region (recipients only).

- Previous number of transplant (recipients only).

Baseline Disease Characteristics include:

- # of HLA –A, –B, –DR, and total mismatches.
- Percent (%) Panel Reactive Antibodies (PRA) (recipients).
- Primary etiology of end stage renal disease (ESRD; recipients only).
- Specific Disease History (recipients).
- Primary cause of death (donors).
- Recipient and Donor EBV antibody serostatus.
- Recipient and Donor CMV antibody serostatus.
- Viral serology for Hepatitis B (donors).
- Viral serology for Hepatitis C (donors).
- T Cell Cross-match for Transplant (recipients).
- B Cell Cross-match for Transplant (recipients).
- Type of transplant (donors).

7.5 Extent of Exposure

The extent of exposure to belatacept will be summarized in two different ways: by total number of active infusions and by length of exposure.

A frequency distribution table will be presented summarizing the total number of active infusions administered in the ranges of 5 infusions for the belatacept treatment group.

In addition, the length of exposure to the assigned treatment will be summarized and presented according to the following time intervals (in days): ≤ 28 (≤ 1 month), 29-84 (2-3 months), 85-168 (4-6 months), 169-252 (7-9 months), 253-364 (10-12 months), 365-448 (13-15 months), 449-532 (16-18 months), 533-616 (19-21 months), 617-728 (22-24 months), ≥ 729 (> 24 months). This summary will also be produced for the TAC treatment group. The number of subjects in each category will be displayed.

For belatacept, the length of exposure will be calculated as the last infusion date + 28 days or death date (if earlier) minus first infusion date.

For TAC, the length of exposure will be calculated as the last infusion dose + 10 days or death date (if earlier) minus first dose date.

All summaries of exposure (both for total number of infusions and length of exposure) will also include a summary of the mean, the standard deviation, the median and the maximum and minimum values (i.e. range).

These analyses will be produced using the as treated population.

7.5.1 Discontinuation of Study Therapy

The ITT analysis population (defined in [Section 6.2](#)) will be used to summarize discontinuation from study therapy by treatment group as indicated in [Section 7.4.1](#) as well as the reason for the premature termination of study therapy.

7.6 Efficacy

This section and its subsections describe the planned efficacy analyses based on data included at the time of the final database lock.

All analyses for efficacy endpoints below will be assessed and described for each of the 2 treatment groups and for the overall study population, unless otherwise specified.

7.6.1 Primary Endpoints

7.6.1.1 Acute Rejection

Rates of acute rejection will be summarized by treatment group at Months 6, 12 and 24 using point estimates of the proportion of subjects experiencing at least one CSBPAR, and the corresponding 95% CIs. Two-sided 95% CIs will also be generated for the difference between the two treatment regimens. Descriptive statistics will be provided for the percentages of subjects with CSBPAR in each treatment group, including those for severity grade and treatment received (corticosteroids, lymphocyte depleting agents, renal replacement therapy, plasmapheresis, IVIg, rituximab). All grades of acute rejection, excluding those assessed by the pathologist as "borderline changes" (biopsy findings "suspicious" for acute cellular rejection per the Banff criteria), will be included in the analysis of the primary and relevant secondary endpoints for acute rejection. Sensitivity analyses will be performed, including acute rejections assessed by the pathologist as 'borderline changes' (biopsy findings "suspicious" for acute cellular rejection per the Banff criteria).

In addition, Kaplan-Meier (KM) cumulative event rates will also be performed by treatment groups and the corresponding hazard ratio will be calculated using cox proportional hazard model for the whole study treatment period (i.e. 24 months).

A corresponding listing including all suspected acute rejection events, regardless of when they occurred, will be provided. All events occurring more than 56 days since last dose date will be flagged.

An additional listing will be produced including subjects who post-CSBPAR, are reported to have developed infection or malignancy.

Sensitivity analyses

Sensitivity analyses will be performed on the PP population as well as on the AT population for the primary analysis, if there are in either treatment group at least 10% of subjects with a protocol deviation or subjects for which the as-randomized treatment group is different for the as-treated treatment group, respectively. The table below is a summary of the analysis along with the populations it will be performed in.

Table 7.6.1.1-1: Overview of Sensitivity Analysis

Measure of Interest	Analysis Method	Sensitivity Analysis Population
Proportion of subjects who experience a CSBPAR at 6, 12 and 24 months post-transplant	Point estimate of the proportion and 95% CI* within each treatment group at 6 months	AT and PP
Difference in the incidence of CSBPAR between arms, at 6, 12 and 24 months post-transplant	Point estimate and 95% CI† for the difference between the two arms	AT and PP
Time to CSBPAR	Kaplan-Meier (KM) estimates of survival functions Hazard Ratio and 95% CI‡	AT and PP

* Confidence Interval Formula: Exact (Clopper-Pearson)

† Confidence Interval Method: Score (Wilson)

‡ Using Cox Proportional Hazard model

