5 SAMPLE SIZE AND POWER

This study is descriptive in nature and is not powered to show statistically significant treatment differences for any outcome measure. A sample of approximately 70 subjects, randomized in a 1:1 ratio to the belatacept + EVL and TAC + MMF groups, is planned.

If the true probability of CSBPAR in the belatacept + EVL treatment group is 3.8%, a sample size of 35 subjects allows the estimation of the population proportion (π) with a 95% CI[†] of 0.2% to 16.4% around the observed proportion of CSBPAR. If the rate is 3%, in the TAC +MMF treatment group, then the 95% CI[†] around the estimate would be 0.1% to 15.1%, for lower and upper limits, respectively.

For the secondary endpoint of assessing the difference in the incidence of CSBPAR at 6 months post-transplantation between the TAC + MMF and belatacept + EVL groups, respectively, with 35 subjects per treatment group, if the observed incidences of CSBPAR (conservatively based on study IM103034) are 3% and 3.8%, the 2-sided 95% confidence interval (CI)* of the differences between the observed incidence rates can be summarized as in Table 5-1:

Table 5-1: Confidence Intervals* for the Difference between Two Proportions

Difference of Treatments (assumed proportions)	Lower 95% Confidence Limit	Upper 95% Confidence Limit	Half Width
TAC + MMF (3%)			
vs.	-13.2%	11.3%	12.25%
Bela + EVL (3.8%)			

[†] Confidence Interval Method: Clopper-Pearson

* Confidence Interval Method Score (Wilson)

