7.6.2 Secondary Endpoints

7.6.2.1 Subject and Graft Survival

A listing will be provided of all subjects who died or experienced graft loss at any time during the study. A listing of all subjects with unknown subject and graft survival status at the end of the 24 month-treatment period will be provided.

If there are at least 5 subjects across treatment groups who died or experienced graft loss during the 24 month-treatment period, the following analyses will be produced:

- The composite endpoints of patient and graft survival at 24 months respectively will be summarized within each treatment groups, using point estimates of the proportion of subjects surviving with a functioning graft, and the corresponding 95% CIs. The point estimate and its 95% CIs will also be generated for the difference between the two treatment regimens.
- The proportion of subjects who die, proportion of subjects who have a graft loss, and the proportion of subjects who experience the following outcomes will each be summarized using point estimates and 95% CI within each treatment group.
 - Overall graft loss rates at 24 months.
 - Rates of death with a functioning graft at 24 months.

- Rates of pure (death-censored) graft loss at 24 months.
- In addition, Kaplan-Meier (KM) estimates of cumulative subject and graft survival rates will also be summarized.
- The subject and allograft survival rates will be summarized among those subjects who did and those who did not experience CSBP. This analysis will be produced only if there are at least 5 subjects across treatment groups who died or experienced graft loss during the 24 month-treatment period.

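### The SAP requires a Cox hazard ratio for time to CSBPAR over 24 months with no event condition or fallback, although an arm with no event is a real possibility and would leave no finite estimate

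*SAP*

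**What the plan says.** SAP 7.6.1.1 (Acute Rejection) adds Kaplan-Meier event rates to the planned proportions and states that "the corresponding hazard ratio will be calculated using cox proportional hazard model for the whole study treatment period", i.e. 24 months. Table 7.2-1 in SAP 7.2, the overview of primary and key secondary analyses, gives the method for time to first CSBPAR as "Kaplan-Meier (KM) estimates of survival functions. Hazard Ratio and 95% CI", with a footnote naming the Cox model. Table 7.6.1.1-1 repeats the row for the as-treated (AT) and per-protocol (PP) populations. None of the three places has an event condition or a fallback.

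The SAP does set such rules elsewhere:

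- **Death or graft loss.** SAP 7.6.2.1 opens its list of analyses with "If there are at least 5 subjects across treatment groups who died or experienced graft loss", and the hazard-ratio row for this endpoint in Table 7.2-1 carries the same condition.
- **Composite of CSBPAR, death or graft loss.** SAP 7.6.2.2 requires at least one CSBPAR and at least one death or graft loss.
- **Proportions.** The text of SAP 7.2 switches from a normal approximation to an exact interval below 5 events.

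The planning rates are in SAP 5: "If the true probability of CSBPAR in the belatacept + EVL treatment group is 3.8%, a sample size of 35 subjects" and "If the rate is 3%, in the TAC +MMF treatment group". The between-arm precision statement there is introduced by "For the secondary endpoint of assessing the difference in the incidence of CSBPAR at 6 months post-transplantation", so these are 6-month rates.

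**The concern.** The expected number of events is very small. When every event falls in one arm, the Cox partial likelihood keeps rising as the log hazard ratio moves towards plus or minus infinity. It has no finite maximum, and an interval built from the standard error at the last iteration means nothing. When neither arm has an event, there is no likelihood to maximise.

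The SAP added Section 7.1 because of the reduced sample size and there limited several analyses to cases with enough events. The CSBPAR hazard ratio was left unconditional, next to a conditioned one in the same table, and no reason is given.

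At stake is the handling of one key secondary output. The trial is open-label. Without a stated rule, the choice to print a divergent ratio, drop it or replace it with another estimator would be made with the events by arm in view.

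**Working it through.** **Inputs.** SAP 5 gives 35 subjects per arm and CSBPAR rates of 3.8% (belatacept + EVL) and 3.0% (TAC + MMF) at 6 months. SAP 7.6.1.1 sets the hazard ratio's horizon at 24 months, and SAP 8.4 defines Month 24 as Day 1 to Day 728. The documents give no 24-month rate.

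**Step 1: the plan's own figures.** Expected events are 35 × 0.038 = 1.33 and 35 × 0.030 = 1.05. Clopper-Pearson limits at these non-integer counts are 0.21% to 16.37% and 0.09% to 15.14%. The SAP states 0.2% to 16.4% and 0.1% to 15.1%. The Wilson-score interval for the difference at 35 per arm is -13.17% to 11.32%, against the stated -13.2% to 11.3%. The inputs are therefore read as the SAP used them.

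**Step 2: chance of an event-free arm at the planning rates.** P(no event in an arm) = (1 - p)^35.

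- Belatacept + EVL: 0.962^35 = 0.258
- TAC + MMF: 0.970^35 = 0.344
- At least one arm: 1 - (1 - 0.258)(1 - 0.344) = 0.513
- Both arms: 0.258 × 0.344 = 0.089
- Exactly one arm: 0.513 - 0.089, about 0.425 before rounding

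Expected events in total are 1.33 + 1.05 = 2.38.

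**Step 3: move to 24 months.** The 0.513 is the chance of an event-free arm by Month 6. It carries over to 24 months only if no subject has a first CSBPAR after Month 6. Otherwise it falls. The multipliers below are assumptions.

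| 24-month rate relative to the 6-month rate | At least one arm with no event | Fewer than 5 events in total |
|---|---|---|
| 1.0 | 51% | 91% |
| 1.25 | 40% | 82% |
| 1.5 | 30% | 71% |
| 2 | 17% | 48% |
| 3 | 5% | 15% |

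Under constant hazard over 24 months, the arm probabilities of no event are (0.962^4)^35 = 0.0044 and (0.970^4)^35 = 0.0141. The chance of at least one event-free arm is then 1 - (1 - 0.0044)(1 - 0.0141) = 0.018, about 2%.

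The last column uses the SAP's own threshold for death or graft loss. By that standard, the CSBPAR hazard ratio would often be withheld.

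**Step 4: what the ordered fit returns.** A Cox fit to 2 events against 0, with 35 per arm, did not converge. The log hazard ratio reached 31.5 with a standard error of about 4.9 million.

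**Step 5: where a remedy is needed.** In simulation, when both arms had events, the ordinary Wald interval covered about 99% or more, so it was conservative. Firth-penalised Cox with a profile-penalised-likelihood interval, with one-arm-zero data sets kept in, covered about 96% to 99% overall. Its log hazard ratio was about 14% to 20% smaller on average. The remedy matters most when exactly one arm has no event.

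**The case against.** The strongest reply is that little depends on this output. The study is descriptive and not powered for any comparison, and SAP 7.2 says that no tests will be done. The primary endpoint is the within-arm proportion at 6 months. The difference in proportions with an interval and the Kaplan-Meier curves are already planned. All of these survive an event-free arm, and a divergent ratio would be obvious beside the event counts. This stands, and it limits the point to a clarification of a secondary output.

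A second reply is that the 5-subject condition for death or graft loss is a poor model. It counts subjects across both arms, so a split of 5 against 0 meets it and still gives no finite estimate. This also stands: copying that condition alone would not close the gap. It does not explain why one hazard ratio in Table 7.2-1 has a sparse-data rule and the other has none.

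Three stronger readings are tempting, and the documents do not support them:

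- **A reader might infer that the 24-month hazard ratio will more likely than not fail to exist.** The 51% rests on 6-month rates. Every assumed multiplier above 1 in the table puts the chance below one half.
- **A reader might infer that the SAP commits to a Wald interval.** It says only that the 95% CI comes from the Cox model. A profile-likelihood interval fits that wording and keeps one finite limit when only one arm has no event.
- **A reader might infer that intervals from one to three events per arm are invalid.** In the simulation they were too wide, not too narrow.

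**Conclusion.** The gap is real and minor. The SAP orders an estimate that has no finite value in a foreseeable situation and says nothing about what to report then, although it has sparse-data rules for other endpoints.

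The chance of that situation is at most about 51% if the 6-month planning rates are true and 35 subjects per arm are analysed. It is about 30%, 17% or 5% at 1.5, 2 or 3 times those rates, and about 2% under constant hazard. The documents do not say which of these applies. Sparse events without an empty arm are likely over much of this range, but they leave the ratio imprecise rather than undefined.

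The consequence is confined to a descriptive key secondary output and its AT and PP repeats.

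**What to change.** In SAP 7.6.1.1, Table 7.2-1 and the AT and PP rows of Table 7.6.1.1-1, add two rules:

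1. If either arm has fewer than 5 CSBPAR events, including none in one arm, the hazard ratio comes from Firth-penalised Cox regression with a profile-penalised-likelihood 95% CI, shown with the event counts by arm.
2. If neither arm has an event, the hazard ratio is reported as not estimable. Only the Kaplan-Meier estimates and the planned interval for the difference in proportions are given.

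The first trigger would be met with probability above 99% at 1 to 2 times the planning rates and about 93% at 3 times. In practice, the penalised fit becomes the expected analysis, and the SAP should say so.

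A minimum alternative is to extend the 5-event condition to this row and also require at least one event in each arm.

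The cost is two sentences and a standard software option. The downside is shrinkage of the log hazard ratio, about 14% to 20% of its mean in the simulation.

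One related conflict should be settled in the same edit. For the difference in proportions with few events, the text of SAP 7.2 calls for an exact interval while Table 7.2-1 names a Wilson score interval, so the planned interval that rule 2 relies on is not uniquely defined.

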7.6.2 Secondary Endpoints

7.6.2.1 Subject and Graft Survival

A listing will be provided of all subjects who died or experienced graft loss at any time during the study. A listing of all subjects with unknown subject and graft survival status at the end of the 24 month-treatment period will be provided.

If there are at least 5 subjects across treatment groups who died or experienced graft loss during the 24 month-treatment period, the following analyses will be produced:

- The composite endpoints of patient and graft survival at 24 months respectively will be summarized within each treatment groups, using point estimates of the proportion of subjects surviving with a functioning graft, and the corresponding 95% CIs. The point estimate and its 95% CIs will also be generated for the difference between the two treatment regimens.
- The proportion of subjects who die, proportion of subjects who have a graft loss, and the proportion of subjects who experience the following outcomes will each be summarized using point estimates and 95% CI within each treatment group.
 - Overall graft loss rates at 24 months.
 - Rates of death with a functioning graft at 24 months.

- Rates of pure (death-censored) graft loss at 24 months.
- In addition, Kaplan-Meier (KM) estimates of cumulative subject and graft survival rates will also be summarized.
- The subject and allograft survival rates will be summarized among those subjects who did and those who did not experience CSBP. This analysis will be produced only if there are at least 5 subjects across treatment groups who died or experienced graft loss during the 24 month-treatment period.

